## 11.2 Source Documents

This study includes data collection and management tools that also meet HIPAA security rules to protect confidentiality and security of protected health information.

**Electronic Health Record (EHR):** Data will be abstracted from the EHR of children including diagnoses (from the child's problem list), basic demographic data, and information on scheduled appointments, missed appointments, screening tools administered, screening results, referrals made, referrals completed, billing codes, and surveys collected through MyChart, the EHR's patient portal. MyChart is an interactive system integrated into the patient EHR (Epic/ OCHIN) and offers patients personalized and secure on-line access to portions of their medical records and also allows providers to send messages and to communicate with patients. MyChart will be used to communicate with families, conduct screening, and monitor symptoms, and track study outcomes / measures. Epic/OCHIN is a fully encrypted, HIPAA compliant system. EHR records at the health center are further protected by firewall

technology. The study investigators will only receive de-identified, ID coded MyChart collected data from DotHouse.

All data will be provided by DotHouse to the study investigators in ID coded form.

FP visit templates: FPs will document in the EHR the details of the eight tasks outlined in protocol manuals: 1) initial encounter, 2) assessment of barriers, 3) plan to address barriers, 4) referrals to service (type and location) 5) confirming appointments scheduled, 6) confirming appointments attended, 7) post-assessment follow-up, and 8) connecting with treatment services. De-identified logs will be scored by study staff to measure the number and nature of completed tasks by the FP.

BACO billing data: We will triangulate BACO billing data with EHR data documenting service use. BACO data will allow us to capture behavioral health services provided outside of DotHouse. BACO billing data will be de-identified by staff at DotHouse who are responsible for maintaining the cross walk between patient name and study ID.

Data from Act.MD: ACT.md allows for data capture and reporting, including patient demographics and assessment data. Dynamic patient-centered care plans and project management functionality allow care teams to track goals, activities, events and referrals. Act.MD also offers panel management capabilities, event notification and tracking, and appointment management capabilities. Data will be abstracted from the Act.MD on care coordination information, frequency of parent and care team use. Act.MD is not part of the EHR and uses patient names. A cross-walk that links study IDs to participants' names will be kept locked at DotHouse and used to link data from Act.MD to data obtained from EHR and billing data prior to releasing these data to the study investigators. Only after obtaining parental release of information, will the FP use Act.MD to coordinate with schools and other care providers outside of DotHouse. Confidential data transmitted outside of DotHouse networks will be encrypted. Transmission of confidential data to an entity outside the DotHouse networks is permitted if the sender has determined that all the following conditions are met: the receiving entity has been authenticated; the receiving entity is aware of the transmission and is ready to receive the transmission; and the sender and the receiver are able to implement a compatible encryption and decryption mechanism. All Act.MD data are encrypted at rest. Because it is possible that we may obtain data from schools, we will ensure that all data collection and data sharing comply with FERPA guidelines.

Procedures will ensure that source data meet the "ALCOA" standards: Attributable, Legible, Contemporaneous, Original, and Accurate.

REDCap: We will be using a web-based database to track upcoming tasks and remind the family partners of tasks they need to complete with each family, such as sending questionnaires to families and upcoming visits. The database application, called REDCap, uses MS SQL Server as the back end relational database. The program can support one or more research studies, is presently being used at dozens of major academic research centers to support numerous NIH funded projects and is available commercially. The HIPAA privacy rules and HIPAA security rules mandate that covered entities have in place appropriate policies and procedures to protect the confidentiality and security of protected health information. In compliance with these regulations, the database security features of REDCap target multiple levels including the data element (e.g. restricted access to fields), user (e.g. password authentication access), application (e.g. role-based access to features, access audit trails), and hosting services (e.g. firewall, secure sockets layer). Taken together, these features ensure access control, audit control, data integrity, user authentication, and transmission security.

BOX: Interview transcripts and recordings will be stored in BOX, a HIPAA compliant cloud storage platform. Once interviews are transcribed and de-identified, the recordings will be destroyed.

### 11.3 Study Records Retention

All study records will be retained for seven years after completion of the study. Documentation of informed consent of subjects will be retained for at least three years after the study is closed. Such records are preserved as a combination of hardcopy, and electronic form and will be accessible for inspection and copying by authorized individuals.

## **12. Statistical Plan**

### **12.1 Study Hypotheses**

Within each factor, we hypothesize that one condition will be more effective in assisting families in accessing mental health services than the other (Enhanced: Technology assisted > usual care; Clinic + Community > Clinic-based; Enhanced: Tracking > Pediatric Surveillance).

### **12.2 Sample Size Determination**

#### **Sample Size and Power.**

Of the three measures to operationalize engagement, we powered our study on the dichotomous variable “receipt of BH services within 90 days” - the most conservative estimate. We base our power calculation on the number needed to detect the smallest differences in primary outcomes that are of clinical importance. Our formative work with staff at DotHouse and other community health centers indicates that a relative risk of approximately 25% would be considered clinically significant. Therefore, if 60% of families in the core navigation condition engage in mental health services (estimates based on our prior work), to detect a 25% difference (i.e. 75% of families in any of the FN delivery conditions engage in services), and assuming 2-tailed tests and a type 1 error rate of 5%, approximately 304 participants are required to detect this effect (n=38 in each of 8 cells). Although 304 participants are required for our power analysis, we will be enrolling 715 human subjects which include 304 parent/legal guardian, 304 index children for primary analysis and around 107 siblings for families with more than one eligible child. Additional sibling analysis will be done to explore differences in service goals etc.

We expect strong effects of study mediators, in particular fidelity variables and variables that are central to our theoretical model, such as increased parent capacity. Following published guidance based on an empirical review, we estimate that our design will have at least 80% power to detect mediation effects where the paths from independent variable to mediator and from mediator to outcome are of at least small-to-medium effect (ES=.26). Given that our mediation analyses are designed to support decisions regarding intermediate outcomes to be tracked for quality control and assurance, effect sizes less than this magnitude are not considered to be clinically important. In contrast, analyses of patient-level treatment moderators are exploratory as we have no evidence to support hypotheses of any effect.

### **12.3 Statistical Methods**

**Overview.** All statistical analyses will be done in SAS (v9.4) and Mplus (v8). Baseline characteristics of parents and children will be compared across experimental conditions to assess balanced randomization. Characteristics include: race/ethnicity, insurance status, primary language, and child characteristics (e.g., screening scores). Because of the minimization procedures we propose to assign participants to experimental conditions, we expect no significant differences on these variables; nevertheless, we will test for differences in baseline characteristics across conditions. Plots and histograms will be used to explore any non-linear relationships in the distributions of these variables across conditions.

**Objective 1: Effectiveness of FN delivery strategies.**

Following an intent-to-treat model, multiple regression models will be used to test hypotheses regarding the main effects of the three delivery strategies and their combined effects on the study's primary outcome, engagement in appropriate mental health services. A series of increasingly complex models will be constructed to address each specific index of outcome. For example, a logistic regression analysis will test receipt of behavioral health services within 90 days. Cox regression (proportional hazards) analyses will then be used to test the effect of each factor on time-to-scheduling date, and then on time-to-receipt of behavioral health services (with *time to third-next-available appointment* included as a covariate). Given that children may be referred to behavioral health services beyond those designated as primary in their initial visit, multi-level models will then be constructed with time-to-receipt of each behavioral health service as an outcome and with services clustered within child. Similarly, engagement in services will first be analyzed with logistic regression using our definition of engagement in care as a binary outcome, with subsequent multilevel models to analyze engagement in multiple services.

For outcomes involving engagement with services, sensitivity analyses will be conducted in which missing data from the EHR is interpreted as failure to engage in services. While we do not hypothesize interactions among the delivery strategies, these will also be explored. Following recommendations for factorial designs, effect coding (not dummy coding) will be used for experimental conditions to assess for interaction. In addition to evaluating effects "at the margins" using all available cells, results for each individual cell will also be reported, as will simple main effects.

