## 2. Protocol Summary

Title:	Optimizing a Paraprofessional, Family Partner Navigation Model for Children
Population:	The study will include 715 participants which include parent/legal guardian, a child and eligible siblings who will be enrolled from DotHouse Health, a Federally Qualified Community Health Center in Boston. We will enroll children ages 3-12 years who screen positive on behavioral health screening tools, - the Preschool Pediatric Symptom Checklist (PPSC) (3-5 years), which is included in the Survey of Wellbeing of Young Children (SWYC) or Pediatric Symptom Checklist-17 (PSC-17) (6-12 years) OR whose parents indicate a behavioral health concern during any pediatric visit. These screening tools are administered as standard of care (SOC). The study enrollment is expected to be 84% ethnic-racial minority families (i.e. primarily Asian, Latino, and African American).
Intervention:	This is a pragmatic optimization trial of Family Navigation (FN), an evidence-based care management strategy which is a promising intervention to help low income and minority families access timely mental health services. Despite significant evidence supporting the effectiveness of FN, concerns exist about the ability to disseminate FN to a broad population due to inefficiency and cost. The current proposal is designed to develop an optimized, efficient, effective, and equitable version of FN to be delivered by trained Family Partners (FP), the goal being to improve access to, and engagement in, diagnostic and treatment services for children with mental health disorders. Specifically, families who participate in the study (includes parent/legal guardian, child and if applicable, additional siblings) will work with one of the trained study Family Partners (FPs) and will be randomized to one of 16 possible strategies to

	deliver FN. FPs will then work with families based on the condition to which they were randomized.

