Objectives:	Our primary objective is to identify which of the FN delivery strategies: (A) use of enhanced technology for care coordination vs. usual care; (B) community and home-based delivery vs. clinic-based delivery only; (C) intensive symptom tracking vs. low level symptom tracking; and (d) individually tailored vs standardized, schedule-based visits with families contribute meaningfully to improvement in the primary outcome - access to child mental health services. We will estimate impact of the 4 delivery strategies and the combinations of these strategies on the study's primary outcome. Based on our findings we will determine the best combination of FN components for evaluation in future randomized trial. Our secondary objectives are to evaluate which components of FN are most effective for whom and the mechanisms related to effectiveness.

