Design/Methodology:	
We will be using a highly efficient experimental design to identify which of the FN components contribute meaningfully to improvement in the primary outcome - access to child mental health services. We will concurrently gather information on FN's mechanisms of effectiveness. The study will take place in the real world context of a community health care center.
 
Children will be enrolled if they have a positive behavioral health screen on one of the age appropriate screening measures (PSC or PPSC) which are universally used in the clinic OR parent report of a behavioral health concern. If agreeable, families will be referred to a FP who will inform families about the study. Families who consent to study participation will be randomized to one of 16 combinations of strategies to deliver FN and will work with the study FP. Families who decline participation in the study will have the option to work with health center care managers (instead of the study FPs) who also offer care coordination. Those families will not be randomized or followed as part of the study.
 
Delivery of FN will be systematically varied across four components, each of which is represented by a separate factor in our 2x2x2x2 factorial study design (See figure 1). Specifically, each family (includes parent/legal guardian, child and if applicable, additional siblings) will be randomly assigned to one of two conditions within each of 4 factors or delivery strategies, defining 16 separate experimental conditions. Strategies include: (A) technology-assisted delivery of care coordination using an innovative, web-based platform called Act.MD (compared to usual care); (B) clinic based FN + community-based (compared to clinic-based only); (C) enhanced symptom tracking using more frequent behavioral symptom tracking by the FP (compared to standard pediatric surveillance); and (d) individually tailored vs standardized, schedule-based visits with families. All children will be followed through the EHR for 12 months, for outcomes in services access and symptom tracking.

We will estimate main effects of the 4 experimental factors and the effects of combinations of the delivery strategies on the study's primary outcome – family engagement in child mental health services.

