## 4. Objectives

### 4.1 Study Objectives

**Primary Objective:** To identify which of the FN delivery strategies: (A) use of enhanced technology for care coordination vs. usual care; (B) community and home-based delivery vs. clinic-based delivery only; (C) intensive symptom tracking vs. low level symptom tracking; and (d) ) individually tailored vs standardized, schedule-based visits with families contribute meaningfully to improvement in the primary outcome - access to child mental health services.

**Secondary Objective:** To evaluate the mechanisms of FN effectiveness and for whom it is effective.

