## 5. Study Design

**Type of study design.** Our design is a factorial experiment utilizing a multiphase optimization strategy (MOST). We will test the effectiveness of 4 FN delivery strategies using a randomized (2x2x2x2) full factorial design.

**Study population and setting.** This study will be conducted at DotHouse Health (DotHouse), a federally qualified community health center in one of Boston's most diverse neighborhoods. DotHouse serves >3,000 children in our target age range, of which >85% are racial/ethnic minority and report incomes ≤200% of the federal poverty level. In addition to medical services, the health center provides comprehensive child behavioral health services. Multilingual, multicultural social workers, licensed mental health clinicians, and a psychiatrist provide behavioral care in an onsite behavioral health department, behavioral health clinicians integrated within the pediatric primary care clinic provide assessment and brief intervention. DotHouse participates in Boston HealthNet, an integrated safety-net care delivery system that includes 13 health centers and Boston Medical Center, which provides primary and specialty care in Boston's urban, low income neighborhoods. In 2018, Boston HealthNet will become part of Boston Accountable Care Organization, a model of care designed to address the "triple aim" of improving patient experience, health, and reducing cost.

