**Rationale for study design and features.** Specifically, we will use *Multiphase Optimization Strategy (MOST)*, a research method borrowed from the field of engineering, which relies on a randomized, multi-factorial design, and therefore facilitates our ability to simultaneously test the effectiveness of three novel strategies and combinations for delivering FN components. The design will also allow us to test varying combinations of FN factors, ranging from what we propose is the least innovative (core FN) to the most innovative (enhanced technology +community visits +enhanced monitoring). We will then evaluate which combinations of factors are most effective and efficient in regards to achieving the primary outcome (engagement in child mental health services). *This is also a pragmatic experiment.* Similar to pragmatic trials, FN will be integrated into routine clinic workflow and supported by standardized visit templates within the electronic health record which will assist with studying implementation and next steps for dissemination into other primary care and community health centers in the future.

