**Figure 3. Full factorial experimental design (3: 2x2x2)**

Group	Experimental conditions			Effects of interest				Notes
	Factor A	Factor B	Factor C	A	B	C	A*B	
1	Standard FN	Standard FN	Standard FN	-1	-1	-1	+1	Least innovative model (standard FN)
2	Standard FN	Standard FN	Enhanced monitoring	-1	-1	+1	+1	
3	Standard FN	Community visits	Standard FN	-1	+1	-1	-1	
4	Standard FN	Community visits	Enhanced monitoring	-1	+1	+1	-1	
5	Enhanced technology	Standard FN	Standard FN	+1	-1	-1	-1	
6	Enhanced technology	Standard FN	Enhanced monitoring	+1	-1	+1	-1	
7	Enhanced technology	Community visits	Standard FN	+1	+1	-1	+1	
8	Enhanced technology	Community visits	Enhanced monitoring	+1	+1	+1	+1	Most innovative model

"Standard FN" = primary care based FN; "Enhanced technology" = additional use web portal ACT-MD; "Community visits" = visits at home or in the community; "Enhanced monitoring" = additional screening conducted by FPs between pediatric visits.

**Randomization Process.** Before initiation of FN and after obtaining parent consent, FPs will randomly assign each family an experimental condition using a computer program. The computer program will use both a randomly-generated number and "minimization procedures" to minimize imbalances across conditions with respect to target variables, including family/child characteristics (e.g., education,

gender, race/ethnicity, screening score). In this procedure, the first participant is assigned at random. Subsequent participants have a  $p$  chance of being randomly assigned and a  $1-p$  chance of being automatically assigned to the condition that would most reduce imbalance based on selected sample characteristics. Minimization procedures are considered best practices for sequential assignment. Families with more than one child enrolled will participate in the same random condition for all children.

**Number of study groups/ arms and descriptions.** Randomization across 4 binary factors results in 16 possible combinations of the 4FN delivery strategies (see **Figure 3**). In total, we plan to enroll 304 families:  $n=19$  for each of the 8 cells. 304 families represent around 715 unique human subjects with 304 parent/legal guardian, 304 index children, 107 additional siblings for families with more than one child enrolled.

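### The primary analysis in 12.3 tests three delivery strategies and omits Factor D, although the primary objective and design have four factors; the stated cell counts do not fit 16 conditions

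*Combined protocol and SAP*

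**What the plan says.** Four factors are set out in several places:

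- Protocol Summary: families "will be randomized to one of 16 possible strategies to" deliver FN. Under Objectives, "We will estimate impact of the 4 delivery strategies and the combinations of these strategies". Under Design, "We will estimate main effects of the 4 experimental factors" on the primary outcome.
- Section 4.1: the primary objective includes Factor D, asking whether "individually tailored vs standardized, schedule-based visits with families contribute meaningfully to improvement in the primary outcome".
- Section 5: "We will test the effectiveness of 4 FN delivery strategies using a randomized (2x2x2x2) full factorial design". Later, "Randomization across 4 binary factors results in 16 possible combinations". Strategy D (visit structure) is listed among the assigned strategies, and Section 8 describes it.

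Other current text describes three factors:

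- Section 12.1 opens with a general statement about every factor, then lists directional comparisons for A, B and C and stops.
- Section 12.3, Objective 1: "multiple regression models will be used to test hypotheses regarding the main effects of the three delivery strategies and their combined effects".
- Section 12.3, Objective 2 names only A, B and C as the strategies whose causal effects the design can test directly.
- Section 12.2 gives 38 in each of 8 cells. Section 5 plans 304 families but gives 19 for each of 8 cells.
- The design rationale in Section 5 says the design can "simultaneously test the effectiveness of three novel strategies and combinations for delivering FN components". Figure 3 tabulates 8 groups with no column for D. Section 8 speaks of eight combinations directly after saying that four components are tested.

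**The concern.** Section 12.3 is the text an analyst would carry out. Read literally, it fits main effects for three strategies, and Sections 12.1 and 12.3 (Objective 2) identify those three as A, B and C. Every family would be randomised on D, yet the plan would contain no named test of D, although D is part of the primary objective and the trial exists to choose the best combination of components. If D's test is not written down in advance, whether D counts as a primary or an exploratory result could be settled after the data are seen.

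A labelling gap goes with this. Section 8 marks one level of A, B and C as enhanced but neither level of D. The documents therefore do not say which level of D is the reference, or what the core navigation condition in 12.2 means for D.

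**Working it through.** **1. The plan's own total.** Inputs from 12.2: 60% versus 75%, two-sided 5%. Power for the primary outcome is not stated; 80% is assumed because it reproduces the plan's figure. The comparison is between the two levels of one factor, pooled over the other factors.

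n per level = [z(0.975)·√(2·p̄·q̄) + z(0.80)·√(p1·q1 + p2·q2)]² / (p2 − p1)², with p̄ = 0.675 and q̄ = 0.325.

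- √(2 × 0.675 × 0.325) = √0.43875 = 0.6624; × 1.960 = 1.298
- √(0.60 × 0.40 + 0.75 × 0.25) = √0.4275 = 0.6538; × 0.8416 = 0.550
- (1.298 + 0.550)² / 0.15² = 151.9 (unrounded terms), so 152 per level and 304 in total

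This matches the stated 304. Power at 152 versus 152 is 80.0%.

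**2. Does adding D change this?** No. In a full factorial each factor splits the same families in two, so each of A, B, C and D compares 304/2 = 152 with 152. Minimization does not guarantee exact equality, and its probability p is not stated. As an illustration, a 142/162 split gives 79.7% to 80.0% power, depending on which level is larger.

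**3. Cell counts.**

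| Source | Per cell x cells | Total | Fits 304? | Fits 16 conditions? |
|---|---|---|---|---|
| Section 12.2 | 38 x 8 | 304 | yes | no |
| Section 5 | 19 x 8 | 152 | no | no |
| 12.2 size, 16 cells | 38 x 16 | 608 | no | yes |
| Section 5 size, 16 cells | 19 x 16 | 304 | yes | yes |

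In Section 5 the wrong number is the count of cells. In 12.2 both 38 and 8 belong to a three-factor layout.

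**4. Effects covered.** Four two-level factors have 2⁴ − 1 = 15 effects: 4 main effects and 11 interactions. Three have 2³ − 1 = 7: 3 main effects and 4 interactions. A model built on three strategies therefore omits D's main effect and the 7 interactions that involve D.

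**5. Where D could still enter Section 12.** Section 12.1 lists A, B and C. The Objective 1 text gives the number three without listing the factors. The Objective 2 text lists A, B and C. D is named in none of them.

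**The case against.** The strongest reply is that the intent is plain elsewhere. The Protocol Summary commits to four main effects, Section 4.1 puts D in the primary objective, and nothing says 12.3 overrides those sections. An analyst handed 16 conditions would probably query the word three rather than drop a factor. Section 12.3 also has general wording that could cover D: its Cox models test each factor, and marginal effects use all available cells. The opening of 12.1 covers every factor without direction, and 12.2 specifies two-tailed tests.

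Parts of this stand:

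- D is arguably under the general hypothesis in 12.1; what it lacks is a listed comparison and a direction.
- With effect coding and a two-sided test, swapping D's levels only reverses the sign of its coefficient. The reference level matters for reporting, not for the test.
- The Objective 2 sentence contrasts randomised factors with mediators, so alone it is weak evidence about the primary model.
- The cell counts change neither the total nor the power per factor.

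The reply does not remove the main point. In 12.3 the general phrases follow the statement that three strategies are tested, so they do not clearly extend to a fourth. The summary shows what was intended; the operative analysis text contradicts it. An analysis plan should not depend on the analyst noticing and correcting its statement of the primary model.

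**Conclusion.** The point holds and must be fixed. As written, the primary analysis covers three of the four randomised factors in the primary objective. This is a wrong statement in the operative text, not merely missing detail. The sentence in 12.3 is the essential correction; the cell counts, Figure 3 and the other three-factor passages are lesser items to reconcile.

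The finding does not claim lost power. The total of 304 and about 80.0% power per factor are unaffected, given the plan's 60% versus 75% at two-sided 5%, near-equal levels, and a power target of 80% that is inferred rather than stated.

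**What to change.** - **12.3, Objective 1:** name A, B, C and D as effect-coded main effects in the primary logistic model, and carry D explicitly into the Cox and engagement models.
- **12.3, Objective 2:** add D to the strategies named in the mediation text.
- **12.1:** add a hypothesis for D, or state that D is tested two-sided with no prior direction. State which level of D is the reference.
- **12.2 and Section 5:** give 304 families as a planned 19 in each of 16 conditions, about 152 per level of each factor. Describe these as expected numbers, since minimization does not guarantee equal cells.
- **Section 5 rationale, Figure 3 and Section 8:** reconcile to four factors and 16 conditions.

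The cost is protocol and SAP wording only. No further families or data are needed, and the total stays at 304.
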